17.1 Sample size calculation

Sample size calculations (for cohort I) are based on an assumption of a standard deviation of 3.1 cm/year for HV after 26 weeks of treatment and the use of a delta value of -3.8 cm/year (where delta corresponds to the non-inferiority margin in a non-inferiority trial) and a one-sided significance level of 2.5%. This results in 15 subjects per treatment arm. Expecting at most 7% dropout during the trial, 15 subjects randomised per treatment arm should assure 87% power for getting a 95% confidence interval for the estimated treatment difference that lies completely above the chosen delta value when comparing a NNC0195-0092 treatment arm to the Norditropin® FlexPro® treatment arm, given that the two treatments are equal.

The addition of cohort II and III is based on a regulatory request from FDA and no formal sample size calculation was performed for these cohorts. The statistical considerations for cohort II and III can be found in section [17.3.2](#) and [17.4.3](#).

17.2 Definition of analysis sets

Three analysis sets are defined.

The Full analysis set (FAS) is defined as all randomised subjects that received at least one dose of randomised treatment. Only in exceptional cases may subjects be excluded from the FAS. Subjects will be analysed “as treated”.

The Safety analysis set (SAS) is defined as all randomised subjects that received at least one dose of randomised treatment. Subjects will be analysed “as treated”.

The Per Protocol (PP) analysis set is defined as subjects from the FAS who have not violated any inclusion/exclusion criteria and have used the randomised treatment for at least 22 weeks (for subjects receiving NNC0195-0092) or 154 days (for subjects receiving Norditropin® FlexPro®) during the main trial period. Subjects will be analysed “as treated”.

The subjects or observations to be excluded, and the reasons for their exclusion must be documented and signed by those responsible before the first pDBL. The subjects and observations excluded from analysis sets, and the reason for this, will be described in the CTR.

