The fixed body weight based regimen has been chosen for this trial as it is standard practice for GH treatment of children with GHD in most countries and the dose for the daily GH comparator in this design is within the upper dose range in the approved labelling.

After the main trial partial data base lock (pDBL) the sponsor will become unblinded while the subjects and site staff will remain blinded with regards to NNC0195-0092 dose level allocation until end of the extension period of the trial. For the safety extension period and onwards all subjects will receive open-label treatment with NNC0195-0092 [REDACTED] mg/kg/week.

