Data management is the responsibility of Novo Nordisk.

Appropriate measures, including encryption of data files containing person identifiable data, will be used to ensure confidentiality of subject data, when they are transmitted over open networks.

Data from central laboratories will be transferred electronically. In cases where data is transferred via non-secure electronic networks, data will be encrypted during transfer.

The subject and any biological material obtained from the subject will be identified by subject number and trial ID. Appropriate measures such as encryption or leaving out certain identifiers will be enforced to protect the identity of subjects in all presentations and publications as required by local, regional and national requirements.

DBLs are planned during the trial, facilitating analysis of the 26 weeks main trial period, 52 weeks extension trial period and 104 and 156 weeks safety extension trial period the 364 weeks long-term safety extension period and the 'extension until NNC0195-0092 is available for prescription for children with GHD period' data. Further interim reporting may be performed in association with marketing authorisation application or in connection with Health Authorities e.g. FDA, EMA and PDMA requirement for/during the regulatory review. The final DBL will occur after the 208 week long-term safety extension trial period (368 weeks) is completed.

16 Computerised systems

Novo Nordisk will capture and process clinical data using computerised systems that are described in Novo Nordisk Standard Operating Procedures and IT architecture documentation. The use and control of these systems are documented.

Investigators working on the trial may use their own electronic systems to capture source data.

17 Statistical considerations

If necessary, a statistical analysis plan (SAP) may be written in addition to the protocol, including a more technical and detailed elaboration of the statistical analyses. The SAP will be finalised before the first pDBL.

Biostatistics, Novo Nordisk, will be responsible for the statistical analyses.

The one-sided test used for the primary endpoint is based on an alpha level of 2.5%. All other statistical tests conducted will be two sided on the 5% significance level. Age group is defined as a factor with 2 levels: <6 years ≥ 6years. No adjustment for multiple testing will be applied.

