17.3 Primary endpoint

17.3.1 Primary endpoint (cohort I)

Height velocity (HV) (cm/year) during 26 weeks of treatment.

Height is measured at baseline, 13 weeks and 26 weeks, and the primary endpoint is derived as:

$HV = (\text{height at 26 weeks visit} - \text{height at baseline}) / (\text{time from baseline to 26 weeks visit in years})$.

For the intermediate visit, annualized HV at 13 weeks is derived similarly: $(\text{height at 13 weeks visit} - \text{height at baseline}) / (\text{time from baseline to 13 weeks visit in years})$.

The primary objective is to evaluate the efficacy of multiple dose levels of once-weekly NNC0195-0092 after 26 weeks of treatment in GH treatment naïve pre-pubertal children with GHD, compared to Norditropin® FlexPro® (once-daily hGH administration), and the primary analysis of the primary endpoint will be the primary tool for achieving this.

Primary analysis of the primary endpoint is based on the FAS.

Annualized HV at 13 and 26 weeks will be analysed using a mixed model for repeated measurements (MMRM), with treatment, age group, sex, region and sex by age group interaction term as factors and height at baseline as a covariate, all nested within week as a factor. An unstructured covariance matrix will be used to describe the variability for the repeated measurements for a subject. From the MMRM the treatment differences at week 26 between NNC0195-0092 treatment arms and Norditropin® FlexPro® will be estimated with the corresponding 95% CI. Subjects without post-randomisation HV data will not be included in the primary analysis.

The analysis will be repeated on the PP analysis set as a sensitivity analysis.

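### The primary height-velocity analysis groups the full analysis set by treatment received, with no rule for a child who took more than one trial treatment and no as-randomised analysis of the full set

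*Combined protocol and SAP*

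**What the plan says.** Section 17.2 defines three analysis sets and has all of them analysed as treated. For the FAS the text reads "Only in exceptional cases may subjects be excluded from the FAS. Subjects will be analysed “as treated". The FAS and the safety set (SAS) share one definition: randomised, with at least one dose of the randomised treatment. The PP set is narrower. It requires no eligibility violation and that subjects on NNC0195-0092 "have used the randomised treatment for at least 22 weeks" (154 days for Norditropin).

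Section 17.3.1 states "Primary analysis of the primary endpoint is based on the FAS". From that model the "treatment differences at week 26 between NNC0195-0092 treatment arms and Norditropin® FlexPro® will be estimated", and the analysis is repeated only on the PP set. Section 17.1 sizes the trial for the same contrasts, "when comparing a NNC0195-0092 treatment arm to the Norditropin® FlexPro® treatment arm".

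Three further statements bear on when the arm of a child with mixed exposure could have been settled:

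- Section 17.2 requires that, for excluded subjects or observations, "the reasons for their exclusion must be documented and signed by those responsible before the first pDBL". This covers exclusions and not arm assignment.
- Section 17 says "If necessary, a statistical analysis plan (SAP) may be written in addition to the protocol", and that any such SAP is to be final before the first partial database lock.
- Section 5.5 says "After the main trial partial data base lock (pDBL) the sponsor will become unblinded".

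**The concern.** Grouping by treatment received is the usual convention for a safety set. Applied to the efficacy set, it lets something that happens after randomisation decide which arm a child counts in, so a contrast with Norditropin need no longer be a purely randomised comparison. The PP analysis does not repair this: it uses the same grouping on a selected subset.

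The plan also leaves the grouping undefined where it would make a difference. If a child took the allocated treatment and another trial treatment during the 26 weeks, the arm could be set by first dose, by longest exposure or by allocation. The threshold of 22 weeks or 154 days decides PP membership only.

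At stake is whether a reader can trust that the week 26 contrasts, from about 14 children per arm, are randomised comparisons. Section 3.2 says the results will inform phase 3 dose selection.

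**Working it through.** **Inputs.** From section 17.1: SD 3.1 cm/year, delta -3.8 cm/year, one-sided 2.5%, 15 randomised per arm, at most 7% dropout, true difference 0, stated power 87%. The documents give no rate of mixed exposure, so moving one child is an assumption.

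**1. The plan's own figure.**
- Completers per arm: 15 × 0.93 = 13.95, taken as 14.
- Standard error: 3.1 × √(2/14) = 1.17.
- Noncentral t with 26 df and noncentrality 3.8/1.17 gives power of 87.7%, which agrees with the stated 87%.
- Grouping as randomised leaves 15 per arm, so this figure does not change.

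**2. Who can be affected.** FAS entry needs a dose of the randomised treatment, so a child who took only another arm's treatment is outside the set. A child who took only the allocated treatment is in the same arm either way. That leaves mixed exposure to trial treatments. A marketed product started after discontinuation is recorded as concomitant medication (section 8.3.3), and a 25% dose-reduction step (section 5.6) is not allocation to another arm. The clearest remaining route is a wrong pen, since section 9.2 makes the blinded NNC0195-0092 pens visually identical.

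**3. Size if one child moves between two NNC0195-0092 arms.** Assume equal raw arm means and a child d cm/year from the mean; 14/14 becomes 13/15.

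| Quantity | Formula | d = 3.1 (1 SD) | d = 6.2 (2 SD) |
|---|---|---|---|
| Shift in the arm losing the child | d/13 | 0.24 | 0.48 |
| Shift in the arm gaining the child | d/15 | 0.21 | 0.41 |

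These are the shifts in two of the three Norditropin contrasts; the third does not move. A child at the mean shifts nothing. The 95% CI half-width is 2.056 × 1.17 = 2.41 cm/year, so the shifts are 9% (0.21/2.41) to 20% (0.48/2.41) of the half-width, and 5% (0.21/3.8) to 13% (0.48/3.8) of delta. These are raw-mean figures; the covariate-adjusted model would differ somewhat.

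**4. Direction.** Simulation of 200,000 trials per scenario, moving one child at random, gives a mean shift of 0.00 and a median absolute shift of about 0.15 cm/year. Whether the CI lies above -3.8 changes in 3.0% to 3.5% of trials per affected contrast when the treatments are equal, and in 5.4% to 6.2% when the true difference is -1 or -2. These changes go both ways. With equal treatments the net chance of passing goes from 87.7% to 86.4% (13 against 14) or to 88.9% (15 against 14), which is the effect of arm size alone. At a true difference of -3.8 it stays at 2.5%.

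**5. The opposite risk.** Suppose the true difference is -3.8 and k of 15 children in one arm cross over fully to the comparator, yet are analysed as randomised. The expected difference is -3.8 × (1 - k/15), which is -3.55 for k = 1 and -3.29 for k = 2. The chance of passing rises from 2.5% to 4.0% and 6.1%. Full crossover is an upper bound, because FAS members took at least one allocated dose.

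**The case against.** The strongest reply is that the wording may affect nobody. The first dose is supervised (section 5.3), the IWRS allocates product at randomisation and at each dispensing visit (section 9.4), and compliance checks include inspection of pens (section 8.9). No child with mixed exposure is reported. Pen strengths are redacted, so one cannot read from the document whether a wrong pen would deliver another arm's dose. A single dispensing error need not last 26 weeks, whereas the illustration moves the child's whole growth record. All of this stands, and it keeps the point small.

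It is also fair that as-randomised grouping is not automatically conservative against a non-inferiority-type delta (step 5). That is a reason to keep an exposure-based analysis beside it, not a reason to have no as-randomised analysis.

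A separate SAP could have supplied the rule. It was optional, none is in the material available, and the compulsory sign-off before the lock does not extend to arm assignment.

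A reader might infer that an arm was chosen after the results were known. The documents do not support that: an SAP had to be final before the first partial lock, and the sponsor was unblinded only after the main-period lock, so a rule could have been fixed blind to dose. A reader might also take the 3.0% to 6.2% of changed conclusions as evidence of bias. They are random movement in both directions around a mean shift of zero.

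**Conclusion.** The point holds as a minor one. The plan groups the primary efficacy set by treatment received, has no as-randomised analysis of the full set, and gives no rule for the only children to whom the grouping makes a difference.

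The effect is zero if no child had mixed exposure. If one child 1 to 2 SD from the mean was moved between two NNC0195-0092 arms, two of the three contrasts shift by 0.21 to 0.48 cm/year. That rests on 14 per arm, SD 3.1, equal raw means and a complete move. Systematic bias would arise only if reassignment were related to growth, and nothing in the documents shows that. The text does not support saying that the primary result is biased or that randomisation was broken; it supports saying that a reader cannot confirm from the plan that every contrast is fully randomised.

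**What to change.** In section 17.2, state that for comparisons of the randomised arms up to week 52, FAS subjects are analysed as randomised. The limit is needed because section 5.1 moves all NNC0195-0092 children to one dose level after week 52. Keep as-treated grouping for the SAS and define which treatment sets the arm of a child with mixed exposure. Retain the as-treated and PP efficacy analyses beside the as-randomised one, so that dilution of a true deficit against -3.8 would be visible.

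Section 3.1.6 describes the main period as complete, so new wording cannot govern that primary analysis. For that period, check the accountability records kept by dispensing unit number (DUN; section 9.4) and report whether any child's analysed arm differed from the randomised arm. Medication-error forms alone are not enough. Under section 12.1 a wrong DUN counts only if the wrong drug was given, and a higher dose only if it exceeded the intended dose by more than 100% and clinical consequences were judged likely. If any child differs, add a labelled as-randomised primary analysis beside the original, not in its place.

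The cost is one sentence, one definition and a check of existing records. No new data are needed, and sample size and power do not change.

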17.3 Primary endpoint

17.3.1 Primary endpoint (cohort I)

Height velocity (HV) (cm/year) during 26 weeks of treatment.

Height is measured at baseline, 13 weeks and 26 weeks, and the primary endpoint is derived as:

$HV = (\text{height at 26 weeks visit} - \text{height at baseline}) / (\text{time from baseline to 26 weeks visit in years})$.

For the intermediate visit, annualized HV at 13 weeks is derived similarly: $(\text{height at 13 weeks visit} - \text{height at baseline}) / (\text{time from baseline to 13 weeks visit in years})$.

The primary objective is to evaluate the efficacy of multiple dose levels of once-weekly NNC0195-0092 after 26 weeks of treatment in GH treatment naïve pre-pubertal children with GHD, compared to Norditropin® FlexPro® (once-daily hGH administration), and the primary analysis of the primary endpoint will be the primary tool for achieving this.

Primary analysis of the primary endpoint is based on the FAS.

Annualized HV at 13 and 26 weeks will be analysed using a mixed model for repeated measurements (MMRM), with treatment, age group, sex, region and sex by age group interaction term as factors and height at baseline as a covariate, all nested within week as a factor. An unstructured covariance matrix will be used to describe the variability for the repeated measurements for a subject. From the MMRM the treatment differences at week 26 between NNC0195-0092 treatment arms and Norditropin® FlexPro® will be estimated with the corresponding 95% CI. Subjects without post-randomisation HV data will not be included in the primary analysis.

The analysis will be repeated on the PP analysis set as a sensitivity analysis.

17.3.2 Primary endpoint (cohort II and III)

The primary endpoint will be used to support the primary objective of evaluating safety of once-weekly NNC0195-0092 during up to 208 weeks of treatment in children with GHD:

- Incidence of adverse events, including injection site reactions

The primary endpoint will be analysed by cohort using descriptive statistics. All adverse events with onset after the first administration of trial product and up until end of trial visit or 14 days after last trial drug administration, whichever comes first, will be included in the analysis. Adverse events with onset 14 days or more after last trial drug administration will be reported in a separate listing.

17.4 Secondary endpoints

17.4.1 Supportive secondary efficacy endpoints (cohort I)

Changes from baseline to end of main trial period (week 26) in the following variables will be used to address the primary objective:

- Height standard deviation score (SDS)
- HV SDS
- IGF-I SDS
- IGFBP-3 SDS

Additionally, scores of the following PRO questionnaires will be used to address the secondary objective of investigating impact of NNC0195-0092 relative to Norditropin® FlexPro® on wellbeing, psychosocial functioning and treatment satisfaction in GH treatment naïve pre-pubertal children with GHD:

- Change from baseline to week 26 in TRIM-CGHD-O: Treatment Related Impact Measure – Child Growth Hormone Deficiency- Observer
- TB-CGHD-O: The Treatment Burden Measure – Child Growth Hormone Deficiency – Observer at week 26
- TB-CGHD-P: The Treatment Burden Measure – Child Growth Hormone Deficiency – Parent/Guardian at week 26

The secondary efficacy endpoints: change in height SDS, HV SDS, IGF-I SDS and IGFBP-3 SDS from baseline will be analysed using an MMRM similar to the MMRM used for the primary analysis of the primary endpoint with baseline assessment as covariate and treatment, age group, sex, region and sex by age group interaction term as factors, all nested within week as a factor. For the PRO based endpoints, this model corresponds to an analysis of variance with treatment, age group, sex, region and sex by age group interaction as factors. For change from baseline in TRIM-CGHD-O, the baseline score value is added to the model as a covariate.

Annualized HV at 39 weeks and at 52 weeks are derived analogous to the HV in the main trial period: (height at d weeks visit-height at baseline) / (time from baseline to d weeks visit in years), where d=39, 52.

Changes from baseline to end of extension trial period (week 52) in the above listed variables (except the two TB-CGHD PROs) will be used to support the secondary objective regarding evaluation of efficacy for up to 364 weeks of treatment and analysed analogously as above using an MMRM based on assessments 13, 26, 39 and 52 weeks (26 and 52 weeks for the PRO based endpoints). From the MMRM the treatment differences at Week 52 between NNC0195-0092 treatment arms and Norditropin® FlexPro® will be estimated with the corresponding 95% CI.

- HV (cm/year) at week 52

HV and the two TB-CGHD PROs at week 52 will be analysed using an MMRM based on assessments 13, 26, 39 and 52 weeks (26 and 52 weeks for the 2 PRO based endpoints) with treatment, age group, sex, region and sex by age group interaction term as factors, all nested within week as a factor. For the analysis of HV, height at baseline will be included in the model as a covariate, also nested within week as a factor. From the MMRM the treatment differences at Week 52 between NNC0195-0092 treatment arms and Norditropin® FlexPro® will be estimated with the corresponding 95% CI.

Changes from end of main trial period (week 26) to end of extension period (week 52) in all of the above mentioned efficacy variables will also be used to support the secondary objective regarding evaluation of efficacy for up to 364 weeks of treatment and will be analysed using descriptive statistics.

- Bone age (X-Ray of left hand and wrist, central assessed according to Greulich & Pyle atlas)¹⁹ progression vs. chronological age
- Serum NNC0195-0092 concentrations and changes throughout the trial

In addition, NNC0195-0092 serum concentrations and changes during the trial and bone age progression vs. chronological age at visit (week 52) will be analysed using descriptive statistics.

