4.2.2 Secondary endpoints (cohort I)

4.2.2.1 Supportive secondary efficacy endpoints (cohort I)

The following endpoints will be used to support the primary and secondary objective regarding evaluation of efficacy:

Changes from baseline (week 0) to end of main trial period (week 26) in the following variables will be used to address the primary objective:

- Height standard deviation score (SDS)
- HV SDS¹ (derived from standing height from baseline (week 0) to week 26)
- Insulin-like growth factor 1 (IGF-I) SDS
- Insulin-like growth factor binding protein 3 (IGFBP-3) SDS

¹ Baseline (week 0) HV SDS is derived from reported pre-trial standing height measured at minimum 6 months and maximum 18 months prior to screening visit to standing height at baseline (week 0)

Changes from baseline (week 0) and from end of main trial period (week 26) to end of extension trial period (week 52) in the following variables will be used to support the secondary objective regarding evaluation of efficacy during the extension period.

- Height standard deviation score (SDS)
- HV SDS (derived from standing height from baseline (week 0) to week 52)
- IGF-I SDS
- IGFBP-3 SDS

The following endpoints will be used to support the secondary objective regarding evaluation of efficacy at week 52:

- HV (cm/year) at weeks 52 (derived from standing height from baseline (week 0) to week 52)
- Bone age (X-Ray of left hand and wrist, central assessed according to Greulich & Pyle atlas)¹⁹ progression vs. chronological age
- Serum NNC0195-0092 concentrations and changes throughout the trial

Additionally, scores of the following patient reported outcome (PRO) questionnaires will be used to address the secondary objective of investigating the impact of NNC0195-0092 relative to Norditropin® FlexPro® on wellbeing, psychosocial functioning and treatment satisfaction in GH treatment naïve pre-pubertal children with GHD:

- Changes in emotional well-being score, physical health score, social well-being score and total score from baseline to week 26 and 52 in TRIM-CGHD-O (Treatment Related Impact Measure – Child Growth Hormone Deficiency- Observer)
- Total score of TB-CGHD-O (The Treatment Burden Measure – Child Growth Hormone Deficiency – Observer) at week 26 and 52.

- Total score of TB-CGHD-P (The Treatment Burden Measure – Child Growth Hormone Deficiency – Parent/Guardian) at week 26 and 52

The scores of the PROs range from 0-100. A lower score indicates a better health state.

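### The week-26-to-week-52 change in HV SDS, and by one section's wording in HV (cm/year), compares two overlapping intervals and does not isolate weeks 26 to 52

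*Combined protocol and SAP*

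**What the plan says.** Section 4.2.2.1 lists four variables (height SDS, HV SDS, IGF-I SDS and IGFBP-3 SDS) for changes to week 52, both from baseline and from week 26. It says that these "will be used to support the secondary objective regarding evaluation of efficacy during the extension period". In the same section, HV SDS for the main period is "derived from standing height from baseline (week 0) to week 26", and the entry for the extension reads "HV SDS (derived from standing height from baseline (week 0) to week 52". HV in cm/year stands in a separate list, and only as a value at week 52: "HV (cm/year) at weeks 52 (derived from standing height from baseline (week 0) to week 52".

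The derivations agree with this. Section 17.3.1 divides the height gain since baseline by the "time from baseline to 26 weeks visit in years". Section 17.4.1 uses the same form for the later visits: "height at d weeks visit-height at baseline) / (time from baseline to d weeks visit in years), where d=39, 52".

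Section 17.4.1 then takes "Changes from end of main trial period (week 26) to end of extension period (week 52) in all of the above mentioned efficacy variables", makes the analysis descriptive, and gives its purpose as supporting the objective on efficacy over up to 364 weeks. HV (cm/year) at week 52 is among the variables named just before, so the wording takes it in. No HV or HV SDS from week 26 to week 52 is defined anywhere for cohort I.

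**The concern.** Height SDS, IGF-I SDS and IGFBP-3 SDS are values at a point in time, so week 52 minus week 26 describes what happened between those visits. A velocity describes an interval. Here the two intervals are weeks 0 to 52 and weeks 0 to 26, and the second lies wholly inside the first.

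The plan does this differently on either side of the extension period. Baseline HV SDS comes from pre-trial height to week-0 height (footnote in Section 4.2.2.1), so the change from baseline to week 26 compares two consecutive intervals. After week 52, Section 17.4.3 starts afresh, with the velocity from week 52 to week 104. Only weeks 26 to 52 have no velocity of their own.

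At stake is how a table is read. Someone shown a change in HV from week 26 to week 52, in cm/year, would naturally take it as the change in growth rate between the two half-years. That reading would understate the change by about half, and would understate any difference between arms in that change by the same factor.

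**Working it through.** The plan states no figure for this change, so there is nothing of its own to reproduce. The 87% power in Section 17.1 concerns the week-26 comparison and does not enter here.

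**Inputs**
- Visit days from Table 2-1, counted from randomisation (Section 8.1): week 26 + 1 day = day 183, week 52 + 1 day = day 365. Each has a window of +3 days, giving days 183–186 and 365–368.
- HV(0–26) and HV(0–52) as derived in Sections 17.3.1 and 17.4.1.
- Half-year velocities for illustration. These are assumed; the documents give none.

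**Algebra for HV in cm/year.** Write t26 and t52 for the times of the two visits.

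HV(0–52) = [HV(0–26) × t26 + HV(26–52) × (t52 − t26)] / t52

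Subtracting HV(0–26) gives

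HV(0–52) − HV(0–26) = [HV(26–52) − HV(0–26)] × (t52 − t26)/t52

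**The factor**
- Nominal visits: (365 − 183)/365 = 182/365 = 0.499.
- Smallest in the windows: (365 − 186)/365 = 179/365 = 0.490.
- Largest in the windows: (368 − 183)/368 = 185/368 = 0.503.
- Multiplier that recovers the half-year change: 1/0.4986 = 2.01 (range 1.99 to 2.04).

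**Illustrations (assumed velocities)**

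| HV(0–26) | HV(26–52) | HV(0–52) | Change between half-years | Planned change (range over windows) |
|---|---|---|---|---|
| 11 | 8 | (11×183 + 8×182)/365 = 9.504 | −3.0 | −1.50 (−1.47 to −1.51) |
| 11 | 9.5 | (11×183 + 9.5×182)/365 = 10.252 | −1.5 | −0.75 (−0.74 to −0.75) |

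**Time weight.** Weeks 0 to 26 carry a time weight of 183/365 = 50.1% in HV(0–52), with a range of 183/368 = 49.7% to 186/365 = 51.0%. This is a weight on the velocity, not a share of the week-52 value. In the two rows above, the share of the week-52 value that comes from weeks 0 to 26 is (11×183)/(9.504×365) = 58.0% and (11×183)/(10.252×365) = 53.8%.

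**HV SDS.** Both intervals start at baseline, so the overlap is the same. The factor above does not carry over, because the reference mean and SD change with age and the documents do not say which age is used for each interval.

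**The case against.** The strongest reply is that little depends on this. The summary is descriptive and supportive, with no test or decision attached, and the derivations are printed beside the endpoints. The factor is nearly the same for every child, so the sign of the change and its ranking across arms are essentially kept. The height SDS change already covers weeks 26 to 52. Heights at weeks 0, 26 and 52 are all collected, so the interval velocity can be derived at any time, approximately as 2 × HV(0–52) − HV(0–26). All of this stands, and it limits the point to a low-cost improvement.

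It is also fair that every number here depends on HV in cm/year being part of the change. Section 4.2.2.1 does not list it; only the broad phrase in Section 17.4.1 brings it in. The figures are therefore conditional on that reading.

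A reader might infer that the plan promises to isolate the extension period and fails to. The documents do not support that. The sentence in Section 4.2.2.1 about the extension period also covers the change from baseline, which cannot isolate weeks 26 to 52 either, and Section 17.4.1 gives the wider purpose of efficacy over up to 364 weeks.

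A separate SAP, which Section 17 makes optional, might define the change more closely. None is among the documents. What the reply does not remove is that the endpoint's name gives no warning that the two velocities overlap, and that the two sections differ on which variables are included.

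**Conclusion.** The point holds, with modest consequence. The planned week-26-to-week-52 change in HV SDS compares overlapping intervals and does not isolate weeks 26 to 52. If HV in cm/year is included, the same applies, and the planned figure is 0.499 of the change in growth rate between half-years (0.490 to 0.503 within the visit windows). That factor follows from the printed derivations and visit days alone; the velocities in the illustrations are assumptions.

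Two stronger readings are tempting and not supported. One is that half of the week-52 value is main-period growth: 50.1% is a time weight, and the share of the value depends on the velocities. The other is that the change in HV SDS is also halved, or reduced by some known amount: only the overlap is shown.

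The primary endpoint, the power, the week-52 MMRM and HV(0–52) as a first-year velocity are not affected.

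**What to change.** In Section 17.4.1:
- Keep the planned figure and label it as a difference of velocities cumulative from baseline.
- Add a supplementary descriptive derivation, HV(26–52) = (height at week 52 − height at week 26) / (years from the week-26 visit to the week-52 visit), with its SDS. Report HV(26–52) and HV(26–52) − HV(0–26) by arm.
- Keep HV(0–52) as the week-52 endpoint.
- Make Sections 4.2.2.1 and 17.4.1 agree on whether HV in cm/year belongs in the week-26-to-week-52 change.

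The addition should be marked as supplementary because of its timing. Section 3.1.6 describes the main period as completed, and Section 5.5 states: "After the main trial partial data base lock (pDBL) the sponsor will become unblinded".

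The cost is one table label, one line of reconciliation and one derived variable from heights already collected. The new variable is noisier than a full-year velocity because it rests on a half-year interval.
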